## The Vaccination Infant Supplementation (VISS) Study

**Randomised placebo-controlled trial investigating the effect of 8 weeks supplementation with probiotics and vitamin D around routine childhood immunisation on infant's ear temperature, growth, and sleeping pattern in 4-24 month-old infants.**

Infant vaccination numbers in the city of Stonnington and Bundoora have declined over that past decade due to concern over the effect of vaccination. There has been increasing concern that vaccination may adversely affect a child's immune system. However, given the nature of vaccine preventable diseases it is understood that the advantages of disease prevention and vaccination in the community are a priority.

Recent evidence shows that Vitamin D and probiotic supplementation has a beneficial effect on a child's immune system.

This project aims to examine the effect of Vitamin D and probiotics on a child's immune function before and after vaccination in a placebo and treatment group. This project will assess temperature daily for 2 months, pre and post immunisation in a supplemented (Vitamin D and probiotic) and placebo group.

### AUSTRALIAN IMMUNISATION SCHEDULE 

The current Australian routine immunisation schedule is:

|           |   |
|-----------|---|
| Birth     | 

• Hepatitis B (hepB)a

  |
| 2 months  | 

• Infanrix hexa: Hepatitis B, diphtheria, tetanus, acellular pertussis (whooping cough), Haemophilus influenzae type b, inactivated poliomyelitis (polio) (hepB-DTPa-Hib-IPV)

• Prevenar 13: Pneumococcal conjugate (13vPCV) • Rotavirus

 |
| 4 months  | 

• Infanrix hexa: Hepatitis B, diphtheria, tetanus, acellular pertussis (whooping cough), Haemophilus influenzae type b, inactivated poliomyelitis (polio) (hepB-DTPa-Hib-IPV)

• Prevenar 13: Pneumococcal conjugate (13vPCV) • Rotavirus

 |
| 6 months  | 

• Infanrix hexa: Hepatitis B, diphtheria, tetanus, acellular pertussis (whooping cough), Haemophilus influenzae type b, inactivated poliomyelitis (polio) (hepB-DTPa-Hib-IPV)

• Prevenar 13: Pneumococcal conjugate (13vPCV)

             |
| 12 months | 

• Haemophilus influenzae type b and meningococcal C (Hib-MenC) • Measles, mumps and rubella (MMR)

  |
| 18 months | 

• Diphtheria, tetanus, pertussis (whooping cough) (DTPa)

• Measles, mumps, rubella and varicella (chickenpox) (MMRV)

  |
| 4 years   | 

• Diphtheria, tetanus, acellular pertussis (whooping cough) and inactivated poliomyelitis (polio) (DTPa-IPV)

  |

### VITAMIN D

Vitamin D is an important immune regulator. Vitamin D receptors are present on immune cells such as B cells, T cells, and dendritic cells. Vitamin D can therefore modulate the innate and humoral immune responses. Patients deficient in Vitamin D are both more susceptible to infection as well as more susceptible to autoimmunity (Aranow 2011).

Infants who are breastfed are recommended 400IU Vitamin D per day as per the American Academy of Paediatrics. This recommendation is based on expert opinion and recent clinical trials measuring biomarkers of vitamin D status (Greer 2004). The Natural Medicines Database Safety information on Vitamin D states: When used long-term, doses should not exceed the tolerable upper intake level

(UL). Infants from 0-6 months should not exceed the UL of 1000 IU daily. Infants aged 6-12 months should not exceed the UL of 1500 IU daily. Children aged 1-3 years should not exceed the UL of 2500 IU daily.

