### **Participants**

#### **Inclusion criteria**

- Group 1 (preferred): Infants who have not yet been immunised (age range: 4-24 months).
- Group 2: Infants who have been immunised (age range: 4-24 months).
- Parents have agreed to have their child immunised.
- Normal infant growth as per WHO growth charts:  
<http://www.education.vic.gov.au/Documents/childhood/parents/mch/mchgrowthboy24mths.pdf>
- <http://www.education.vic.gov.au/Documents/childhood/parents/mch/mchgrowthgirl24mths.pdf>
- No tympanic temperature > 38 degrees Celsius in the preceding 4 weeks prior to immunisation
- Infants currently breastfed (e.g. exclusively or breast and formula fed)
- Infants currently not taking supplements (Vitamin D and/or probiotics)
- Infants who will remain in the same routine with primary carers for the 2 month study period
- Willing to contribute 50% (\$30) of the cost price for ear thermometer

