### **Intervention/ Comparison**

Sample size: n=50

Active group: n=25

Placebo group: n=25

**Active group:** 1000 IU Vitamin D & 2.3g Probiotics daily for 2 months

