#### **Enrolment & randomisation**

The doctor and chief investigator TN will meet patients at the NIIM clinic to confirm eligibility and to collect the infant's care givers informed consent. Two groups will be recruited into this pilot study, group 1: vaccination-naïve (not yet immunised) infants 4-24 months into the study, and group 2: vaccinated infants 4-24 months.

Eligible infants will be enrolled and randomised. A computer-generated permuted block randomisation schedule prepared by a researcher not involved in patient recruitment and data collection will be used to allocate patients to the active or placebo groups.

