#### **Trial medication**

The active treatment group (n=25) will be allocated to 1000 IU Vitamin D (Metagenics) + 2.3 g probiotics (Inner Health Kids, Metagenics) daily for 2 months. The control group (n=25) will be allocated to matching placebo drops and powder. Placebo drops and powder, supplied by Metagenics, will be matched in quantity and appearance (odour and colour). Care givers of participating infants will be advised to provide the trial supplements with food in the morning.

Drops and powder can be mixed into the infant formula. If infant is exclusively breastfed, the drops can be given directly into the mouth, the powder can be mixed into water and supplied by spoon.

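### Under 6 months the flat 1000 IU dose uses the whole upper intake level the protocol quotes, yet infants also fed formula may enter

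*Protocol*

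**What the plan says.** The Protocol's VITAMIN D section introduces its safety limits with the words "When used long-term, doses should not exceed the tolerable upper intake level". It then gives a limit for each age band. The youngest band reads "Infants from 0-6 months should not exceed the UL of 1000 IU daily". For the second half of the first year the wording becomes "Infants aged 6-12 months should not exceed the UL of 1500 IU daily", and at 1-3 years the level is 2500 IU a day. The same section cites 400 IU a day as the recommendation for breastfed infants.

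Under Intervention/ Comparison the active arm receives "1000 IU Vitamin D & 2.3g Probiotics daily for 2 months". The Trial medication section repeats this dose. Neither place varies it by age or feeding.

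Inclusion criteria set the age range at 4-24 months. They bar other vitamin D sources in supplement form ("Infants currently not taking supplements (Vitamin D and/or probiotics") but accept either feeding pattern: "Infants currently breastfed (e.g. exclusively or breast and formula fed". Trial medication expects formula to be in use: "Drops and powder can be mixed into the infant formula".

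Under Enrolment & randomisation, the doctor "will meet patients at the NIIM clinic to confirm eligibility". The baseline list, given under Assessments and again under Visit 1, asks about the mother's vitamin D but has no item on how the infant is fed. The diaries cover temperature, sleep and crying, and carer sleep.

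**The concern.** An upper intake level applies to total intake. The protocol recognises this in part, because it excludes infants already taking vitamin D supplements. For infants under 6 months the trial product fills the level by itself, so the one further source that the criteria expressly admit, formula, can only add to an intake already at the limit. Nothing in the listed assessments would show that this had happened: no item records formula volume, and no infant vitamin D level is measured. At stake is a safety margin in the youngest healthy infants of a pilot study. The trial's comparison between arms is not affected.

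**Working it through.** **Dose check.** The product entry gives a 90 mL bottle, 0.25 mL per 1000 IU dose and 360 days' supply. 90 / 0.25 = 360 doses, so one 1000 IU dose a day is confirmed.

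**Room left by age** (quoted level minus trial dose):

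| Age | Quoted level, IU/day | Dose as share of level | Room, IU/day |
|---|---|---|---|
| 0-6 months | 1000 | 1000/1000 = 100% | 0 |
| 6-12 months | 1500 | 1000/1500 = 67% | 500 |
| 1-3 years | 2500 | 1000/2500 = 40% | 1500 |

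**Time in the zero-margin band.** Days on product before 6 months = min(56, (6 - entry age) x 30.44).
- Entry at 4 months: 2 x 30.44 = 60.9, capped at 56 days.
- Entry at 5 months: about 30 days.
- Entry at 5.5 months: about 15 days.
- Entry at 6 months: 0 days.

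**Size of the excess.** Formula content and volume are not in the documents, so both are assumed. Excess = volume x content, as a share of 1000 IU.
- Low: 100 mL at 40 IU per 100 mL = 40 IU, or 4%.
- High for an infant also breastfed: 400 mL at 60 IU per 100 mL = 240 IU, or 24%.
- Extreme: 800 mL at 60 IU per 100 mL = 480 IU, or 48%. This is unlikely in an infant who is also breastfed.
- A second set of assumptions, 0.25-0.75 L a day at 200-500 IU per litre, gives 50-375 IU, or 5-38%.

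The size depends on the assumptions. The direction does not, for any formula that contains vitamin D.

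**Check at 6-12 months.** The extreme case gives 1000 + 480 = 1480 IU, inside 1500 IU by 20 IU. At 850 mL and 60 IU per 100 mL the total is 1000 + 510 = 1510 IU, just over. The 500 IU of room covers most plausible formula intakes but is not a guarantee.

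**Number of infants.** If entry ages are even over 4-24 months, the share entering before 6 months is 2/20.
- Active arm: 25 x 2/20 = 2.5. With 20-80% mixed-fed (assumed), 0.5-2 infants are exposed to the excess.
- Both arms, since eligibility precedes randomisation: 50 x 2/20 = 5. The same range gives 1-4 infants who would be declined.
- If instead half of the 50 entered before 6 months: 25 x 0.2 to 25 x 0.8 = 5-20 declined.

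**The case against.** The strongest reply is that the protocol keeps to what it quotes. The dose equals the level and does not pass it, the warning concerns long-term use, and no infant is dosed for more than 8 weeks. This is right as far as it goes. A reader might infer that the protocol contradicts itself or overdoses infants; the documents support neither. They do not show that a short excess breaches the quoted limit. However, the protocol does not use the long-term qualifier to justify its dose either.

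Second, the documents nowhere say that formula contains vitamin D. That is correct, and every excess figure above is conditional on it. The documents alone establish only the zero margin and the admission of formula-fed infants.

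Third, a reader might infer that nobody looks at feeding. Eligibility is confirmed in person and the criterion names both feeding patterns, so formula use is knowingly admitted. The forms and diary pages are not available for review. What can fairly be said is that no listed item records formula volume and no rule acts on it.

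Fourth, the count of infants is fragile. Requiring current breastfeeding and preferring unimmunised infants may well pull entry towards younger ages. That raises both the number exposed and the number a restriction would exclude.

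Finally, a lower dose under 6 months would leave real room: 400 IU, the figure the protocol quotes for breastfed infants, leaves 1000 - 400 = 600 IU and excludes nobody. It is a legitimate alternative, but it gives the youngest infants a different treatment and needs a second matched placebo volume.

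**Conclusion.** The point holds as a cheap improvement. While active-arm infants are under 6 months, the fixed dose leaves 0 IU below the protocol's own quoted level, and the entry criteria admit infants with a further likely source. On the stated formula assumptions the excess is about 4-24%, for at most 56 days. About 0.5-2 of 25 active infants would be affected if entry ages are even and 20-80% are mixed-fed, and more if entry skews young. This is a thin margin, not a demonstrated harm. Breast milk and solids are not assessed, because the documents give no vitamin D content for them.

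**What to change.** 1. In Inclusion criteria, do not enrol infants who are under 6 months at first dose and receive formula containing vitamin D.
2. Add feeding type and usual daily formula volume to the baseline list, under both Assessments and Visit 1, so that the rule can be applied.
3. Tell carers to contact the study doctor before starting formula while the infant is under 6 months, so that the drops can be stopped until 6 months. The instruction is identical in both arms and keeps the blind.
4. Vaccinate declined infants promptly outside the trial. Unimmunised infants of this age have already missed the 2-month doses in the national schedule.

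Raising the entry age to 6 months is not advised. With vaccination at week 4, the earliest in-trial first dose would move from 4 + 28/30.44 = 4.9 months to 6 + 28/30.44 = 6.9 months.

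The cost is a short amendment: one eligibility line, two baseline items and one carer instruction. About 1-4 of 50 infants become ineligible on the even-age assumption, and 5-20 if half would have entered before 6 months. The results would not cover mixed-fed infants under 6 months. Arms, starting dose and analysis are unchanged. The rule removes formula as a source only; it creates no margin for exclusively breastfed infants under 6 months.

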## PROBIOTICS

Probiotics are also important in both the innate and humoral immune responses. Probiotics can modulate the function of dendritic cells, macrophages and B and T cells (Yan 2011). Probiotics given to infants during vaccination may increase their seroconversion rate (del Giudice 2014).

Infants from 3 months recommended 2.3g (1 tsp) of probiotic blend containing: 6 billion *Lactobacillus rhamnosus*, 3.75 billion *Lactobacillus acidophilus* and 3.75 billion *Bifidobacterium lactis*. There are multiple studies which have included these probiotics in infants 3 months and over which have demonstrated safety of use (Gritz 2015, Saavedra 2007).

## **STUDY DESIGN**

Randomised parallel double-blind placebo-controlled trial of 2 months duration investigating the effect of supplementation with vitamin D and probiotics on behavioural and physiological response in infants during routine childhood immunisation.

### **Participants**

#### **Inclusion criteria**

- Group 1 (preferred): Infants who have not yet been immunised (age range: 4-24 months).
- Group 2: Infants who have been immunised (age range: 4-24 months).
- Parents have agreed to have their child immunised.
- Normal infant growth as per WHO growth charts:  
<http://www.education.vic.gov.au/Documents/childhood/parents/mch/mchgrowthboy24mths.pdf>
- <http://www.education.vic.gov.au/Documents/childhood/parents/mch/mchgrowthgirl24mths.pdf>
- No tympanic temperature > 38 degrees Celsius in the preceding 4 weeks prior to immunisation
- Infants currently breastfed (e.g. exclusively or breast and formula fed)
- Infants currently not taking supplements (Vitamin D and/or probiotics)
- Infants who will remain in the same routine with primary carers for the 2 month study period
- Willing to contribute 50% (\$30) of the cost price for ear thermometer

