### **Visit 2 – week 4 – vaccination**

The infant will only be eligible to be vaccinated if its temperature had been less than 38 degrees Celsius in the 4 weeks prior vaccination and since enrolment (at week 0).

Eligibility will be assessed by phone call 1-2 days before the scheduled appointment by NIIM receptionists.

If the infant had run a temperature > 38C in the last 4 weeks, the appointment will be postponed until 4 weeks after the fever.

If eligibility criteria are met, the original appointment will be confirmed.

1) **Assessments:** Weight, growth, temperature, other symptoms, collection of infant home diary and carer sleep diary; Carer: Mood Q; Tolerability & compliance Q

2) **Vaccination:** first immunisation of the Australian standard paediatric immunisation schedule:

a) **Infanrix hexa:** combined Diphtheria-Tetanus-acellular Pertussis (DTPa), hepatitis B, poliovirus and haemophilus influenzae type B vaccine

b) **Prevenar 13:** Pneumococcal polysaccharide conjugate vaccine, 13-valent adsorbed

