***Infanrix hexa and Prevenar 13 Information sheets will be provided by TN to the participating carers.***

➤ Immunisation to be given by same medical doctor and investigator TN for all participants.

3) Supply of supplements for 4 weeks – and discussion of administration

Supply of diary: Daily 7pm temperature, infant sleep/cry

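### Already-immunised infants (group 2) are admitted without a requirement that a dose be due at week 4, and the only vaccination described at Visit 2 is a first immunisation

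*Protocol*

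**What the plan says.** The protocol's STUDY DESIGN section sets out to study the "behavioural and physiological response in infants during routine childhood immunisation". Two kinds of infant may enter, both aged 4–24 months: a preferred group not yet immunised, and "Group 2: Infants who have been immunised (age range: 4-24 months"). Enrolment & randomisation repeats this, naming "group 2: vaccinated infants 4-24 months" as the second group.

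Two other inclusion criteria bear on an in-study dose. Parents must have agreed to immunisation, and there is a fever condition: "No tympanic temperature > 38 degrees Celsius in the preceding 4 weeks prior to immunisation".

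Visit 2 at week 4 is headed as the vaccination visit. Its stated condition is about fever: "The infant will only be eligible to be vaccinated if its temperature had been less than 38 degrees Celsius". The content of the vaccination is the "first immunisation of the Australian standard paediatric immunisation schedule", itemised as Infanrix hexa and Prevenar 13. A note after it reads "Immunisation to be given by same medical doctor" and applies this to every participant.

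The Analysis section compares the mean of daily data over weeks 4–8, called after vaccination, with weeks 0–4, called before vaccination. It makes no exception for either group. Sample size & Justification gives 50 infants, 25 per arm, as a pilot to supply starting levels and variability for a larger trial.

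**The concern.** Visit 2 fits group 1 but not group 2. An infant who has already been immunised cannot have a first immunisation, and the protocol names no other dose for that visit. The inclusion criteria do not ask whether a dose will fall due at week 4, the pre-visit telephone check concerns temperature only, and the listed baseline items do not include immunisation history.

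Staff following the text have two courses with a group 2 infant who is not due the named pair. They can give it off schedule, or they can depart from the text by giving another vaccine or none. If none is given, weeks 4–8 are still labelled post-vaccination. The trial asks how supplementation alters the response around immunisation, so including infants with no immunisation weakens any such effect and mixes different kinds of infant in the variance estimate.

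**Working it through.** **The plan's own figure.** The sample size of 50 comes with no effect size, standard deviation or power. There is nothing to reproduce, and no stated figure depends on this point.

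**The texts side by side.**

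| Place in the protocol | What it fixes for group 2 | What it leaves open |
|---|---|---|
| Inclusion criteria, group 2 | Already immunised, 4–24 months | Doses received; whether one is due |
| Inclusion criteria, parental agreement | Immunisation is accepted | Product, dose number, date |
| Inclusion criteria, fever | No fever in the 4 weeks before a dose | Whether a dose is due |
| Visit 2 | First immunisation, named pair | Any dose for a vaccinated infant |
| Note on who immunises | The same doctor throughout | Product |
| Analysis | Weeks 4–8 count as after vaccination | Infants with no dose |

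**The schedule.** The protocol's AUSTRALIAN IMMUNISATION SCHEDULE lists the named pair at 2, 4 and 6 months. At 12 months it lists Hib-MenC and MMR. At 18 months it lists DTPa and "Measles, mumps, rubella and varicella (chickenpox) (MMRV"). The next entry is at 4 years (48 months).

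**Age at Visit 2.** Without postponement, Visit 2 is 28 days after enrolment: 28 / 30.4375 = 0.92 months. Enrolment at 4–24 months gives Visit 2 at 4.92–24.92 months, a span of 20 months. For an infant who is up to date:

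| Next scheduled dose | Arithmetic | Months | Share of the age span |
|---|---|---|---|
| The named pair (6-month dose) | 6 − 4.92 | 1.08 | 5.4% |
| Other vaccines (12 or 18 months) | 18 − 6 | 12.0 | 60.0% |
| Nothing until 4 years | 24.92 − 18 | 6.92 | 34.6% |

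In the last row the next dose is at least 48 − 24.92 = 23.1 months away. Timing enrolment to a coming dose therefore does not cure the mismatch for up-to-date infants. After the 6-month dose the named pair is never next, and after the 18-month dose nothing is.

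**A second measure.** Count a dose as due if Visit 2 falls within a stated distance of its scheduled age (4, 6, 12 or 18 months).

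- Within 0.5 month: the pair covers 1.0 / 20 = 5% of the span, and any dose covers 3.0 / 20 = 15%.
- Within 1 month: the pair covers about 2.08 / 20 = 10.4%, and any dose covers about 6.08 / 20 = 30.4%.

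Both measures describe the permitted age span for an up-to-date infant. They are not proportions of the infants who would enrol.

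**What no-dose infants would do (all inputs assumed).** Let g be group 2's share of the 50 and s the share of group 2 given no dose, so u = g × s.

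- With g = 0.2–0.6 and s = 0.1–0.5, u runs from 0.02 to 0.30, or 1 to 15 of 50 infants.
- If the supplement effect exists only in vaccinated infants, the difference retained is 1 − u, or 98% to 70%.
- If vaccination shifts the before/after change by d standard deviations, the variance is multiplied by 1 + u(1 − u)d². For d = 1: 1 + 0.02 × 0.98 = 1.02 up to 1 + 0.30 × 0.70 = 1.21. For d = 0.5: 1.005 up to 1.05.

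These figures show direction and form only; none of g, s or d is in the protocol.

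**The case against.** The strongest reply is that a pending dose is plainly intended. The parental-agreement criterion applies to every infant and has little meaning where nothing remains to be given. The title, the study design statement and the heading of Visit 2 point the same way. A doctor confirms eligibility in person, and the doctor who immunises is the same throughout, which is a practical safeguard against a dose that is not due. This stands as to intent, and it narrows the gap. It does not fill it, because none of these texts fixes a product, a dose number or a date.

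Infants behind schedule are also plausible here. The protocol describes declining vaccination in the catchment, and its preferred group is unimmunised at 4–24 months. Group 2 infants with the pair outstanding would be served by Visit 2 apart from the word first. So would an infant enrolled at 4 months with the 4-month dose held back. The breastfeeding criterion may also favour younger infants. All of this stands, and it means the age-span figures cannot be read as a rate of mismatch. The protocol does not, however, restrict group 2 to such infants.

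A reader might infer from the note on who immunises that every participant must receive the named pair. The note settles who gives the injection, not which product. A reader might also infer that the comparison of arms is biased. It is not, because group 2 infants are randomised like the rest.

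Finally, handling of unvaccinated infants in the analysis could sit in an SAP. Eligibility and the vaccine given at a visit are protocol matters, and no analysis can supply a dose that was not given.

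**Conclusion.** The concern holds as an inconsistency between who may enter and what Visit 2 provides. Group 2 is admitted, the only vaccination described cannot literally apply to it, and weeks 4–8 count as post-vaccination regardless. The consequence is a possible off-schedule dose, a dose the protocol does not name, or a window that follows no dose. The last dilutes any vaccination-related effect and mixes the level and variance estimates that are the pilot's stated purpose.

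The size is unknown, because group 2's share of the 50, its ages and its vaccination status are not given. It would be tempting to conclude that about 95% of group 2 would meet the wrong vaccine, or that up to 30% of the trial would be mislabelled. The documents support neither: the first figure assumes up-to-date infants spread evenly over the age range, and the second rests wholly on assumed shares.

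The conclusion rests on the text available. The drawings under TIME LINE and FLOW CHART could not be read and may separate the groups at Visit 2; if so, the Visit 2 text should be brought into line with them. The change should be made, since it affects who enters and what they receive.

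**What to change.** 1. Inclusion criteria, group 2: add that a scheduled or outstanding dose is due at Visit 2 (week 4), confirmed from the immunisation record before randomisation.
2. Visit 2: keep the first immunisation with the named pair for group 1, and state that group 2 receives the dose then due.
3. Record the vaccine and the date given for every infant.
4. Keep all infants in the comparison as randomised, including any who in the end receive no dose.

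The cost is one eligibility line, one look at the immunisation record and one reworded line at Visit 2, with somewhat slower recruitment of group 2, which is not the preferred group. Up-to-date infants past the 18-month dose would no longer qualify. Group 2 would still receive a mixture of vaccines, but the mixture would be on record and could be described when the pilot's estimates are used.

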**TIME LINE**

**Appointments with doctor:**

**Outcome measures**

| Primary (1), Secondary (2) | Outcome measures         | Tests        | Equipment                         | Lab/ location | Time points              |
|----------------------------|--------------------------|--------------|-----------------------------------|---------------|--------------------------|
| 1                          | Tympanic ear temperature | Temp         | Thermometer                       | NIIM, home    | Daily incl 0, 4, 8 weeks |
| 1                          | Weight, Growth           | scales       | Growth chart, weight chart        | NIIM          | 0,4,8 weeks              |
| 2                          | Sleep / cry              | Q/ diary     | Daily diary for infant collection | NIIM, home    | Daily                    |
| 2                          | Other symptoms           | Q            | Colds, mouth ulcers, rashes       | NIIM, home    | 0,4,8 weeks              |
| 2                          | Mood/ Stress             | Bond Lader Q | Main carer                        | NIIM          | 0,4,8 weeks              |
| 2                          | Sleep                    | Q            | Main carer                        | home          | Daily                    |

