#### **Visits & Assessments**

##### **Visit 1 – week 0 - baseline**

Enrolment, informed consent by GP and chief investigator TN.

Baseline data collection:

- Infant's mother's Vit D supplementation & plasma levels (if known) – during pregnancy and current
- Birth week of gestation, prematurity
- Vaginal, or caesarean birth
- Vit K given to infant at birth?
- Any genetic screening or other test results
- Infant's medication, e.g. PPI for reflux

Assessments: weight, growth, temperature, other symptoms, Carer: Mood Q

Supply of supplements for 4 weeks – and discussion of administration

Supply of diaries: Daily 7pm temperature, infant sleep/cry = infant home diary; Carer sleep diary = Length and Quality of sleep recorded daily)

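### The fever-free inclusion criterion covers on-treatment weeks 0–4, so it cannot be checked at enrolment, and it conflicts with the Visit 2 rule that only postpones vaccination

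*Protocol*

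**What the plan says.** In the Protocol, Inclusion criteria, one of the conditions for entering the trial is "No tympanic temperature > 38 degrees Celsius in the preceding 4 weeks prior to immunisation". Under Enrolment & randomisation, "Eligible infants will be enrolled and randomised". The Visit 1 section (week 0) covers enrolment and the first hand-out of product: "Supply of supplements for 4 weeks – and discussion of administration". Treatment is "1000 IU Vitamin D & 2.3g Probiotics daily for 2 months" (Intervention/ Comparison). Immunisation belongs to the visit headed "Visit 2 – week 4 – vaccination".

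The Visit 2 section restates the temperature rule as a condition for being vaccinated: the infant's temperature must have been "less than 38 degrees Celsius in the 4 weeks prior vaccination and since enrolment (at week 0"). It is checked by telephone one or two days before that visit. The consequence of a fever is given as: "If the infant had run a temperature > 38C in the last 4 weeks, the appointment will be postponed until 4 weeks after the fever".

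The Outcome measures table marks tympanic temperature as primary, recorded "Daily incl 0, 4, 8 weeks"; weight and growth are also marked primary. The Analysis section compares the average of the daily readings over weeks 4–8 with the average over weeks 0–4, calling the first period after vaccination and the second before it.

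**The concern.** An inclusion criterion decides who may be randomised, so it has to be answerable at that moment. This one concerns the weeks that follow randomisation, while the infant is taking active product or placebo, and it is a threshold on a variable that is itself a primary outcome.

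Two things are at stake. First, an infant with a fever in week 2 has failed an inclusion criterion under one section and is merely waiting for a later appointment under another. A site or analyst who follows the first section would remove randomised infants because of their own on-treatment temperature, and that undoes the protection of randomisation if the supplement affects fever. Second, even where the infant simply stays in the study, the date of vaccination depends on on-treatment temperature, while the Analysis section labels its periods by fixed week numbers.

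**Working it through.** **Timing.** Immunisation is at week 4 (Visit 2) and the window is the preceding 4 weeks. 4 − 4 = week 0, which is enrolment, randomisation and first supply (Enrolment & randomisation; Visit 1). The overlap with on-treatment weeks 0–4 is complete. The Visit 2 section confirms this by tying the rule to the time since enrolment.

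**Status of a randomised infant with a fever in weeks 0–4.**

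| Protocol section | What follows |
|---|---|
| Inclusion criteria | Fails a condition of entry, after entry |
| Visit 2 | Vaccination postponed; no withdrawal stated |
| Exclusion criteria, closing paragraph | Withdrawal, but only for factors in the exclusion list; fever is not one |

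The sections also differ at exactly 38.0 °C. Such a reading passes the inclusion criterion, does not meet the Visit 2 condition for vaccination, and does not trigger postponement.

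**Reading A: the inclusion criterion is enforced.** The only documented input is 25 + 25 = 50 infants. All fever risks below are assumptions.

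- Equal risk p in both arms: the expected number failing is 50p, so 5, 10, 15 or 20 for p = 10%, 20%, 30% or 40%. At p = 10% the chance of at least one case is 1 − 0.9^50 ≈ 0.995.
- Supplement assumed to halve the risk: the number remaining per arm is 25(1 − p).

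| Active v placebo risk | Remaining, active v placebo |
|---|---|
| 10% v 20% | 22.5 v 20 |
| 15% v 30% | 21.25 v 17.5 |
| 20% v 40% | 20 v 15 |

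Dropping these infants makes the weeks 0–4 fever difference zero by construction. To show the effect on later weeks, suppose infants differ in fever-proneness (a gamma-distributed rate with shape 1, Poisson episodes, same rate in both periods). The mean number of later episodes is then p/(1 − p) in all infants, but p in those fever-free in weeks 0–4. The active-minus-placebo difference becomes:

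- 10% v 20%: 0.111 − 0.250 = −0.14 in all infants; 0.10 − 0.20 = −0.10 in those kept
- 15% v 30%: 0.176 − 0.429 = −0.25; 0.15 − 0.30 = −0.15
- 20% v 40%: 0.250 − 0.667 = −0.42; 0.20 − 0.40 = −0.20

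A simulation of the same model gave the same values to two decimals. The direction is towards no effect, under this model only.

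**Reading B: postponement only.** All 25 v 25 remain. A single fever on day d (1 to 28) moves vaccination from day 28 to day d + 28, a delay of d days; the mean is 14.5 days if d is uniform. If weeks 4–8 are counted from enrolment (days 28 to 56), d of those 28 days fall before vaccination: a quarter for d = 7, half for d = 14, all of them for d = 28. The first 4-week supply also runs out d days before the postponed visit, which has to be reconciled with daily treatment for the whole study period.

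**The case against.** The strongest reply is that the Visit 2 section already settles the matter. It speaks of being eligible for vaccination, not for the trial, and it prescribes postponement. The withdrawal rule after the Exclusion criteria is confined to exclusion factors. On that view the inclusion list merely previews a vaccination precondition. Most of this stands: no section withdraws a febrile infant or omits one from the analysis. A reader might infer that the trial will lose more infants from one arm and be analysed on, say, 15 v 20; the documents do not support that as a prediction. It needs both enforcement of the inclusion criterion and fever rates that appear nowhere.

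A reader might also infer that the lack of a fever screen before week 0 biases the comparison. It does not: illness present before allocation is balanced by randomisation in expectation and adds only noise to the weeks 0–4 mean. Such a screen is a design preference.

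Two smaller points are fair. Temperature is one of two outcomes marked primary, and the analysed quantity is a mean reading, not the occurrence of a value above 38 °C, although both come from the same daily measurement. And analysis sets are commonly left to the SAP, which is not at hand. But entry criteria and their timing are protocol content, and the Protocol does fix the analysis periods by week number. One could read those week labels as moving with the visits; the text does not say so, and the before period would then last 28 + d days in postponed infants.

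**Conclusion.** The point holds in a limited form. Three things are certain from the text: the criterion cannot be assessed at enrolment; it and the Visit 2 section give a randomised febrile infant different statuses; and postponement makes vaccination timing depend on on-treatment temperature while the analysis periods carry fixed week labels. The size of the last effect is a shift of 1 to 28 days per affected infant, assuming a single fever and weeks counted from enrolment. How many infants are affected is unknown; assumed risks of 10% to 40% give 5 to 20 of 50.

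Selective loss of randomised infants is a risk conditional on how the inclusion criterion is applied, not something the Protocol prescribes. This should be corrected even in a pilot, because the Sample size section says the study is meant to supply baseline values and variance for a larger trial, and selection on temperature or misaligned periods would distort those values.

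**What to change.** 1. Reconcile the Inclusion criteria with the Visit 2 section, so that the pre-immunisation temperature rule is a condition on vaccination timing only and not a condition of trial entry. If the sponsor wants a fever criterion for enrolment, its window must end at or before week 0. Reconcile the two wordings at exactly 38.0 °C as well.
2. State that no randomised infant is withdrawn, or left out of the analysis, because of temperatures in weeks 0–4.
3. In the Analysis section, define the before and after means from the actual date of vaccination, with the length of each period stated.

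The clinical rule on when a febrile infant may be vaccinated, and how supply is handled during a postponement, are for the sponsor to settle. The cost is a few sentences of protocol text and slightly more work to derive the periods for postponed infants; the sample size and the measurements are unchanged.
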